
D2. Study Population & Eligibility Criteria

The study will be based at the ambulatory obstetrical practices of Baystate Medical Center, a large tertiary care facility in Western Massachusetts that serves a socioeconomically diverse population; 4,300 infants are delivered annually, 57% are Hispanic (predominantly from Puerto Rico with ~58% having income <\$15,000 per year). Eligible women will be Hispanic, overweight or obese (BMI >25 kg/m²), and 16-45 years of age. We will exclude women with 1) prepregnancy BMI <25 kg/m², 2) history of type 2 diabetes, heart disease, or chronic renal disease, 2) contraindications to participation in moderate physical activity or to a low-fat/high-fiber diet (e.g., Crohn's disease, ulcerative colitis), 3) inability to read English or Spanish at a 6th grade level, 4) <16 or >45 yrs of age, 5) >20 wks gestation, 6) current medications which adversely influence glucose tolerance, 7) not planning to continue to term or deliver at the study site, or 8) pregnant with twins or triplets. Women who have a very early preterm birth (<34 wks), a miscarriage, or a still birth after enrollment or a stillbirth will be excluded. Women who become pregnant again in the year following delivery will be censored at the time of their positive pregnancy test.

D3. Recruitment, Baseline Assessment, and Sample Size

Bilingual (Spanish and English) and bicultural health educators will recruit women at the first prenatal care visit (~10 wks gestation). Women will be informed of the aims/procedures of the project, sign an informed

consent, and complete a screening form to determine eligibility. The baseline assessment will be collected via standardized questionnaire and the pregnancy blood sample will be taken (see Figure 1). Expectations for the study and a contacts schedule (face-to-face meeting, mailings, booster telephone calls) will be reviewed. Each assessment and interview completed is associated with a gift card for a total of up to \$360, to be handed out after completing the study component.

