- 2) the postpartum face-to-face meeting takes place at the routine 6 wk postpartum visit and adherence is facilitated by bus passes, cafeteria vouchers, and the 2006 Mass insurance reform law providing free health care insurance for residents earning <150% of the federal poverty level. However, if a woman does not intend to attend this visit, the health educator will meet the women at locations outside the hospital, with consideration for the participant's and the health educator or assessors level of comfort (i.e., their pediatrician's office, their home, a community center). Locations will be selected for privacy (for example, an unused exam room at a pediatrician's office) and only staff who have experience making home visits will be permitted to complete home visits.
- 3) The 6 mos and 1 yr postpartum assessments will be conducted in the hospital or at a location outside the hospital with consideration for the participant's and the health educator or assessors level of comfort
- 4) Approximately 5% of participants in our prior pregnancy cohorts left the Springfield area after delivery; however, travel funds are budgeted for assessors to travel to the broader tri-state area (MA, NY, CT) if necessary.
- 5) Delivering the intervention does not rely upon women remaining in the immediate area during the postpartum year as it is based upon tested mailed print-based materials and telephone contacts. In addition to providing home/cell/work numbers, women will be asked to provide the contact information for a person close to them. Pre-paid cell phone time will be provided as an additional incentive.

D.5. Randomization

Immediately prior to randomization (~12 weeks GA), participants will be evaluated for study inclusion by answering if their provider has restricted their physical activity during this pregnancy. If they answer yes, their medical records will be reviewed by [name] (Co-Investigator, and Director of Maternal/Fetal Medicine at Baystate). Eligible patients will be randomized into either the Lifestyle Intervention vs. the Health and Wellness Comparison Group. Randomization will be stratified based on age (<30, >30 years) and pre-pregnancy BMI (overweight >25-<30 kg/m² vs. obese >30 kg/m²). Within each strata, a blocked randomization will be used such that both treatment groups will be assigned an equal number of times in each set of 4 sequentially enrolled patients.

D.6. Intervention

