Pre-pregnancy BMI, weight at delivery, and gestational age at delivery will be abstracted from the medical record. Gestational age at delivery is recorded by the obstetrician at the time of delivery based on sonograms, date of last menstrual period (LMP), date the first fetal heart beat was heard with a stethoscope, and fundal height. Pregnancy weight is measured prospectively from all participants at each prenatal visit and postpartum weight will be measured by trained study staff to the nearest 0.1 kg on accurately calibrated standard clinical scales using a standardized protocol. Gestational weight gain will be calculated as the difference between maternal weight at delivery and pre-pregnancy weight. Rate of weight gain will be calculated as the difference between maternal weight at delivery and pre-pregnancy weight, divided by gestational age at delivery in weeks. Compliance with IOM weight gain guidelines will be calculated by comparing the observed weight gain with the 2009 IOM Guidelines⁷⁵ at that gestational age. Compliance will be specified as a continuous variable (percent of 2009 IOM Guidelines met) or as a categorical variable: inadequate, adequate, and excessive. Finally, we will measure the area under the gestational weight gain curve (AUC) since the time of randomization.¹⁵⁴ The AUC incorporates in a single statistic not only the final weight but also the trajectory to reach it and has been found to be a predictor of birthweight outcomes.¹⁵⁴ Postpartum weight loss will be calculated as: 1) absolute weight change at 6 and 12 mos postpartum according to pre-pregnancy BMI, 2) percentage who retain a specific amount of weight over pre-pregnancy weight, and 3) proportion whose BMI category changes from pre-pregnancy BMI category as have others.⁵⁹⁻⁶¹

D.12.4. Covariates

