Specific Aim #1, 2, 3: Impact of a Lifestyle Intervention on GWG and postpartum weight loss; biomarkers of insulin resistance; postpartum biomarkers of CVD risk. The primary analysis will evaluate differences in the change from baseline in weight gain measures, glycemia and other biomarkers of insulin resistance and cardiovascular risk factors between the groups (an intent to treat analysis). Initial analyses will describe the correlation of factors and investigate simple transformations for normality. The primary analysis will be based on a mixed model with random subject effects, including a common mean at baseline for the intervention groups, a period effect, and an intervention by period interaction.¹⁷⁰ The intervention by period interaction is a measure of the intervention effect, and corresponds to the estimate of an intervention effect in an analysis of covariance. The mixed model analysis will enable inclusion of time varying covariates such as depression, breastfeeding behaviors, and sleep, which may vary between baseline and follow-up for subjects. Equivalence of the intervention groups will be assessed by comparing the distribution of the potential confounders between each group. We will investigate established risk factors for weight gain (e.g., parity) and glycemia as well as degree and treatment for abnormality on glucose tolerance testing during pregnancy (e.g., diet, oral hypoglycemic and/or insulin) as potential confounders or effect modifiers. Generally, we will consider a change in the parameter estimate for the exposure (at least 15%), relative to that observed when not controlling for the variable as reflective of confounding. Effect modification will be evaluated by inspection of stratum specific odds ratios as well as by evaluating the statistical significance of interaction terms via likelihood ratio tests. We will also model the relationship between measured levels of exercise, sedentary behavior, and diet with each outcome, while adjusting for possible confounders using mixed effect linear regression models. We will test hypotheses with 2-sided tests. Finally, we will compare adoption and maintenance of behavior change (i.e., exercise, diet) in the intervention group relative to the control group by adding a fixed treatment group effect.

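### Gestational weight gain counts gain from before randomisation, and the plan neither says which weight is baseline nor specifies an adjustment for that early gain: missed precision, not bias

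*Combined protocol and SAP*

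**What the plan says.** Section D.12.3 defines the outcome: "Gestational weight gain will be calculated as the difference between maternal weight at delivery and pre-pregnancy weight". The rate of gain divides the same difference by gestational age at delivery, and compliance compares observed gain with the 2009 IOM guidelines. The section adds a measure with a later start: "we will measure the area under the gestational weight gain curve (AUC) since the time of randomization". It also says "Pregnancy weight is measured prospectively from all participants at each prenatal visit".

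Recruitment is at about 10 weeks (D3) and randomisation at about 12 weeks (D.5). The gestational-age exclusion in D2 is ">20 wks gestation". Randomisation is stratified by age and pre-pregnancy BMI (D.5).

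The primary model in D.16 is a mixed model "including a common mean at baseline for the intervention groups, a period effect, and an intervention by period interaction". Its interaction term is said to be one that "corresponds to the estimate of an intervention effect in an analysis of covariance". Potential confounders are judged by whether they move the estimate by at least 15%. Neither the covariate list in D.12.4 nor D.16 names weight at randomisation, gain before randomisation, gestational age at randomisation or the strata as model terms.

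In D.17, Table 3 lists GWG with N 300, SD 7.00 kg and a detectable difference of 2.3 kg. The SD column is for change from baseline.

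**The concern.** Weight gained before randomisation cannot differ by arm except by chance. When the outcome runs from pre-pregnancy weight, that early gain adds between-woman variation that carries no information about the intervention, and a chance imbalance in early gain or entry week passes into the estimate. A covariate measured before randomisation can remove much of this, and the plan already collects the values needed. The cost of omitting it is a wider confidence interval for the outcome listed first under Aim 1.

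Whether the loss occurs depends on a term that the plan leaves open. If baseline weight is pre-pregnancy weight, the common-baseline model adjusts for a value that comes before the early gain, so the early gain stays in the residual. If it is the weight at about 10 to 12 weeks, most of the early gain is handled, but the change analysed is then not the GWG that D.12.3 defines.

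**Working it through.** **1. Reproduce the stated figure.** Inputs from D.17: SD 7.00 kg, 150 per arm, two-sided 5%, power 80%.

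Detectable difference = SD × √(2/n) × (z₀.₉₇₅ + z₀.₈₀) = 7.00 × √(2/150) × (1.960 + 0.842) = 7.00 × 0.1155 × 2.802 = 2.26 kg. With the noncentral t distribution it is 2.27 kg. Both round to the stated 2.3 kg, and power at 2.3 kg is 81%.

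D.17 assumes that covariates explain 20% of the variation in multiple regression models. With that credit the figure would be 2.26 × √0.80 = 2.03 kg, so the tabulated 2.3 kg takes no covariate credit.

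**2. Which weight is baseline?** Two readings are possible.
- *Pre-pregnancy weight.* Table 3 gives the SD of GWG as an SD of change from baseline. D.12.3 measures GWG from pre-pregnancy weight, so baseline would be that weight.
- *Weight at about 10 weeks.* D3 places the baseline assessment at recruitment, and D.12.1 dates the baseline blood sample at about 10 weeks.

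The first reading fits GWG better, but the documents do not settle it.

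**3. Effect of adjusting for early gain.** Let r be the correlation between gain before randomisation and total GWG. The documents do not give it, so its values here are assumptions. Residual SD = 7.00 × √(1 − r²), and the detectable difference shrinks by the same factor from 2.27 kg.

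| Assumed r | √(1 − r²) | Detectable difference (kg) | Variance removed, r² |
|---|---|---|---|
| 0 | 1.000 | 2.27 | 0% |
| 0.3 | 0.954 | 2.17 | 9% |
| 0.5 | 0.866 | 1.97 | 25% |

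**4. Cross-check by another route.** Fix the total SD at 7.00 kg. Let s₁ and s₂ be the SDs of early and later gain and ρ their correlation, so that 49 = s₁² + s₂² + 2ρs₁s₂. The residual SD after adjustment is s₂√(1 − ρ²). The values of s₁ and ρ are again assumptions, and these results use the normal approximation (2.26 kg unadjusted).

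| s₁ (kg) | ρ | R² | Detectable difference (kg) |
|---|---|---|---|
| 1 | 0 | 0.02 | 2.24 |
| 2 | 0 | 0.08 | 2.17 |
| 3 | 0 | 0.18 | 2.05 |
| 4 | 0 | 0.33 | 1.86 |
| 2 | −0.2 | 0.007 | 2.26 |
| 2 | +0.3 | 0.30 | 1.89 |

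The saving is almost nil if early gain varies little or is negatively correlated with later gain. It can exceed a quarter if early gain varies widely or the two are positively correlated.

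**5. Would the 15% rule bring the covariate in?** Not reliably. The rule reacts to a change in the estimate, which in a randomised comparison depends mainly on chance imbalance. A strongly prognostic covariate that happens to be balanced barely moves the estimate and could be dropped, although it would narrow the interval.

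**6. Is modelling delivery weight the same thing?** Write D for delivery weight, P for pre-pregnancy weight and W for weight at randomisation. The model (D − P) = a + b(W − P) + arm rearranges to D = a + bW + (1 − b)P + arm. Adjusting D for W alone drops P and matches only if b = 1.

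**The case against.** The strongest reply is that the plan does adjust for baseline. Its primary model is of analysis-of-covariance type, the word baseline elsewhere refers to the early-pregnancy assessment, and one weight measure starts at randomisation. This stands in part: a reader might infer that the plan makes no adjustment at all, and the documents do not support so flat a statement. What they support is that the baseline weight is undefined and no adjustment for early gain is specified.

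Other stronger readings are tempting and also fail.
- *The estimate is biased.* Early gain precedes randomisation and is balanced in expectation. Chance imbalance is already reflected in the standard error.
- *The trial is underpowered for GWG.* The 2.3 kg uses the full SD of 7.00 kg with no covariate credit, and it reproduces.
- *The GWG definition is wrong.* Total gain from pre-pregnancy weight suits the IOM comparison and the trial's goals, which are set by pre-pregnancy BMI.
- *Up to half of the outcome is noise.* On a nominal 40-week pregnancy, 12 weeks is 30% and 20 weeks is 50%, but these are shares of time, not of weight gained. The 50% applies only at the eligibility ceiling.
- *A known saving is forgone.* No figure in the documents fixes the correlation, and the gain beyond other covariates that might enter the model is unknown.
- *This is the primary outcome.* GWG is the first listed. D.16 puts several outcomes under its primary analysis and singles out none.

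**Conclusion.** The point holds as a missed gain in precision together with an ambiguity to resolve. GWG and its rate include gain from before randomisation. The more natural reading of Table 3 makes pre-pregnancy weight the baseline, and on that reading the planned model leaves early gain in the residual. For an assumed correlation of 0 to 0.5 between early and total gain, the detectable difference would go from about 2.27 kg down to as little as 1.97 kg, with between none and a quarter of the variance removed. That range is an assumption, not a finding from the documents. On the other reading of baseline, most of the loss disappears, but the analysed quantity and the defined outcome then need reconciling. The case for acting is that the values precede randomisation and are already collected, so prespecified adjustment is safe and costs almost nothing even if the benefit proves small.

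**What to change.** - Keep the GWG definition for the IOM comparison.
- State in D.16 which weight is baseline in the weight models.
- In the continuous GWG and rate models, prespecify these covariates: pre-randomisation gain (last measured prenatal weight before randomisation minus pre-pregnancy weight), gestational age at randomisation, and the age and BMI strata. Retain them whatever the 15% change-in-estimate rule shows.
- If delivery weight is modelled instead, include both pre-pregnancy weight and weight at randomisation.
- For the IOM category, use the same covariates but report a standardised (marginal) risk ratio or risk difference. D.17 states its target as a 30% reduction in risk, and a conditional odds ratio from a logistic model would not match it.

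The cost is wording in the analysis section. Prenatal weights are recorded at each visit (D.12.3), the date of the last menstrual period is held (D.15), and the strata are known at randomisation (D.5). No new data are needed and the sample size does not change.

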We will consider the following factors as covariates: Social Support for diet and exercise will be measured via the Social Support for Exercise (SSE). The SSE has three subscales (Family, Friends, Rewards/Punishments) and acceptable internal consistency (alphas .61-.91) and criterion validity.¹ Clinical Characteristics of the Current Pregnancy: will be abstracted from the medical record utilizing customized software developed in our previous studies. Variables include: degree of abnormality on glucose tolerance testing during pregnancy defined as: 1) normal results on the screening 50-g OGTT; 2) failed screening test with normal results on the diagnostic 100-g test; 3) impaired glucose tolerance (IGT) defined as failed screening test and exceeded <1 cutpoints on the 100-g test; and 4) GDM defined as failed 50-g test and exceeded 2 or more cutpoints on the 100-g test;¹⁶³ treatment for abnormal glucose tolerance during pregnancy (e.g., diet, oral hypoglycemic and/or insulin); other pregnancy complications (e.g., hypertensive disorders, preterm birth, infection, cesarean delivery, NICU admission, Apgar score). Medical History: will include: personal history of GDM, family history of diabetes, previous infant with anomalies, still birth, or macrosomia, infertility, and parity. Sociodemographic Factors: will include income, level of education, and health insurance; acculturation via the Psychological Acculturation Scale,¹⁶⁴ language preference, and generation in the U.S. Smoking and Substance Use: Alcohol consumption, smoking, and drug use will be collected via questions from the Pregnancy Assessment Monitoring System.¹⁶⁵ Sleep: Pregnancy and postpartum sleep will be collected via The Pittsburgh Sleep Quality Index (PSQI).¹⁶⁶ Depression: Pregnancy and postpartum depression will be assessed via the Edinburgh Postpartum Depression Scale¹⁶⁷ validated in Hispanics.¹⁶⁸ Breastfeeding: History of breastfeeding and frequency and duration of current breastfeeding (i.e., exclusive breast feeding, % of mixed breast and formula feeding, exclusive formula feeding), timing of introduction of solids, and other breastfeeding behaviors and beliefs will be assessed via the validated Infant Feeding Questionnaire.¹⁶⁹ Postpartum Urine

Pregnancy Test and Postpartum Diabetes Screening (using ADA diagnostic criteria¹⁶³) will occur at each postpartum assessment.

D.12.5. Measures of Adherence

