Specific Aim #4: Evaluate the impact of a Lifestyle Intervention on the outcomes of offspring. We will evaluate the impact of intervention arm on the offspring outcomes using the methods described for Aim #1-3. We will also examine GWG and prenatal glycemic factors as predictors of glycemia and weight gain in early infancy and childhood. Important covariates are listed in the covariate section. In models focused on offspring weight gain as the outcome, we will additionally adjust for fetal growth (i.e., BW/GA z score).

Specific Aim #5: Evaluate the cost-effectiveness of the Lifestyle Intervention. We will use procedures developed in our prior studies examining the cost-effectiveness of our interventions.¹⁷¹⁻¹⁷³ We will calculate the ratio of average dollars spent per average incremental improvement in outcome (i.e., GWG, postpartum weight retention, and biomarkers of insulin resistance and CVD risk). Incremental improvement will be defined as the mean change score from baseline for each group, adjusted for baseline values of the outcome measure and other participant characteristics.

Accounting for Missing Data: Although every effort is made to avoid missing data, we plan to use propensity score techniques¹⁷⁴⁻¹⁷⁶ to evaluate the potential sensitivity of results to missing at random assumptions. Multiple comparisons will be addressed by carefully considering the biologic rationale of observed associations.

D.17. Power

To achieve power to detect clinically significant differences requires 300 participants (150 in each intervention arm) at the time of delivery. Based on observed rates in our 2 trials (R01DK074876 and

ASPH/CDC S3948), we conservatively expect 10% of women to leave the New England area, deliver elsewhere, or withdraw during pregnancy, and therefore will recruit 333 women over the 24 mos recruitment period. For offspring outcomes, we calculate that 4% will be excluded for very early preterm birth (<34 wks), miscarriage, or stillbirth resulting in 288 children at delivery. Over the following 1 yr, we conservatively project that an additional 8% of women will be lost to follow-up due to withdrawal or movement out of the New England area. Women who become pregnant again will be censored. Therefore, we expect 264 women and children at 1 yr postpartum.

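### Minor free improvement: the stated primary model omits the two randomisation factors (age group and pre-pregnancy BMI class), and the plan does not say whether they will be adjusted for

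*Combined protocol and SAP*

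**What the plan says.** - **D.5, Randomization:** "Randomization will be stratified based on age (<30, >30 years) and pre-pregnancy BMI" class, with blocks of four inside each stratum. Two factors at two levels make four strata.
- **D.16, Aims 1 to 3:** the primary mixed model has random subject effects, "including a common mean at baseline for the intervention groups, a period effect, and an intervention by period interaction". The interaction is the measure of effect and "corresponds to the estimate of an intervention effect in an analysis of covariance".
- **D.16, covariates:** time-varying covariates may be added. Known risk factors for weight gain (parity is the example) and for glycaemia will be examined as confounders or effect modifiers. The criterion is: "we will consider a change in the parameter estimate for the exposure (at least 15%), relative to that observed when not controlling" for the variable. The text does not say that a flagged variable enters the primary model.
- **D.12.4, Covariates:** the list opens "We will consider the following factors as covariates" and runs from social support to breastfeeding. It names neither maternal age nor pre-pregnancy BMI.
- **D.16, Aim 4:** "We will evaluate the impact of intervention arm on the offspring outcomes using the methods described for Aim #1-3", and "Important covariates are listed in the covariate section".

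Two other passages come close but do not settle it. D.12.3 expresses one postpartum weight measure by pre-pregnancy BMI, which defines an outcome and is not a model term. Aim 5 adjusts a change score for unnamed participant characteristics, but only for cost-effectiveness. The plan therefore says neither that the strata will be in the primary model nor that they will not.

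**The concern.** Stratified blocking makes the arms alike on age group and BMI class, so the true sampling error of the arm difference no longer contains the variation between strata. A model without the strata still counts that variation as residual noise. If the strata are prognostic beyond baseline, its standard error is too large, its test falls below the nominal 5%, and its interval is wider than the design earned.

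The plan's only covariate criterion does not repair this. It looks for a shift in the arm estimate, which is the mark of confounding. Stratified blocking largely removes that shift for these two factors, however prognostic they are. At stake is a small amount of precision, and a decision on adjustment that is better fixed before the data are seen.

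**Working it through.** **Inputs from D.17.** Two-sided 5% level; 80% power; 300 women (150 per arm) for gestational weight gain (GWG) and glucose; 288 offspring (144 per arm) at delivery; SDs of 7.00 kg (GWG change), 13.27 mg/dl (glucose change) and 640 g (birthweight). Recruitment: "therefore will recruit 333 women over the 24 mos recruitment period". The R-squared of the strata is not given, so every value below is assumed. The 20% that D.17 gives to all covariates together serves as the ceiling.

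**Step 1: the plan's own figures.** Detectable difference without covariates = SD × (1.960 + 0.842) × √(2/n per arm). For GWG this is 7.00 × 2.802 × √(2/150) = 2.26 kg, or 2.27 using the t distribution. On the t basis:

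| Outcome | Computed | Printed |
|---|---|---|
| GWG (kg) | 2.27 | 2.3 |
| Postpartum weight loss | 2.08 | 2.1 |
| Glucose (mg/dl) | 4.31 | 4.3 |
| Systolic pressure (mm Hg) | 4.23 | 4.2 |
| Birthweight (g) | 212.0 | 212 |

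With 20% of variance removed, GWG would be 2.27 × √0.8 = 2.03 kg and birthweight 212.0 × √0.8 = 189.6 g. These printed figures are therefore unadjusted and do not depend on the strata being in the model. Not every figure reproduces. Caloric intake gives 21.1 against 22.4 (the printed value fits 264 women, not 300), and CRP gives 1.56 against 1.5. For exceeding the IOM guidelines, 51% against 0.7 × 51% = 35.7% with 150 per arm gives 76.5% power, not 80%.

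**Step 2: closed form, outcome with no baseline value, exact balance.** With R² the share of variance due to the strata:
- interval ratio, without to with strata = 1/√(1 − R²)
- true type I error without strata = 2 × [1 − Φ(1.960/√(1 − R²))]
- power without = Φ(0.842/√(1 − R²)); power with = Φ(2.802/√(1 − R²) − 1.960)

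At R² = 5%, √0.95 = 0.9747. Power without is Φ(0.864) = 80.6%, power with is Φ(0.914) = 82.0%, and the gain is 1.4 points.

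| Assumed R² | 1% | 2% | 5% | 10% | 20% |
|---|---|---|---|---|---|
| Interval wider without strata (%) | 0.5 | 1.0 | 2.6 | 5.4 | 11.8 |
| Type I error without strata (%) | 4.9 | 4.8 | 4.4 | 3.9 | 2.8 |
| Power gain (points) | 0.3 | 0.5 | 1.4 | 2.7 | 5.3 |

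**Step 3: why a baseline value shrinks the gain.** Suppose the strata explain R² of a level at both visits, with within-stratum correlation ρ. The correlation between visits is r = R² + (1 − R²)ρ. The share left to the strata after baseline is 1 − (1 − R²)(1 − ρ²)/(1 − r²). For R² = 10% and ρ = 0.5, r = 0.55 and the share is 1 − 0.675/0.6975 = 3.2%. It is 5.1% at ρ = 0.3 and 1.7% at ρ = 0.7 (all ρ assumed).

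**Step 4: simulation with blocking and loss.** There were 20,000 trials per setting: 333 women randomised in blocks of four within four strata, and 300 or 288 retained at random. Assumed: 25% in the older group, 55% obese, R² shared equally by the two factors. GWG used baseline weight as a covariate, with BMI classes 20 kg apart and SD 11 kg within class. Glucose used ρ = 0.5. Birthweight had no other covariate. True differences were 2.26 kg, 4.3 mg/dl and 212 g.

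| Assumed R² | 1% | 2% | 5% | 10% | 20% |
|---|---|---|---|---|---|
| GWG gain (points) | 0.2 | 0.5 | 1.0 | 2.2 | 4.9 |
| Birthweight gain | 0.2 | 0.6 | 1.6 | 2.9 | 5.7 |
| Glucose gain | 0.1 | 0.1 | 0.4 | 0.6 | 1.5 |
| GWG interval wider (%) | 0.3 | 0.7 | 1.9 | 4.1 | 9.2 |
| Birthweight interval wider | 0.5 | 1.0 | 2.6 | 5.4 | 11.8 |
| Glucose interval wider | 0.1 | 0.3 | 0.8 | 1.6 | 3.2 |

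Type I error without strata was about 4.7% to 5.0% at R² of 1% to 5%, with a simulation error of about 0.15 points. At 20% it was 3.6% (GWG), 3.0% (birthweight) and 4.3% (glucose).

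**Step 5: the 15% criterion.** If it were used to admit the strata, it would recover at most about 0.1 power points at R² up to 10%.

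**The case against.** The strongest reply is that little is lost. There is no bias, the error is on the conservative side, and at 1% to 5% the gain is at most 1.6 points. Even at the 20% ceiling, simulated GWG power without strata is 82.7%, above the planned 80%. All of this stands, and it is why the point is minor.

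The risk-factor clause in D.16 gives only an example, so age and BMI could fall under it. That also stands, but the clause does not pre-specify them and it leads only to the 15% criterion.

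The birthweight figures compare strata with no covariates at all. Aim 4 points to the D.12.4 list, which includes parity and glucose tolerance. If such variables are in the model, they may already carry part of the stratum information, so the birthweight gains are upper figures.

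The simulation used one follow-up value, whereas the fix adds period interactions for repeated outcomes. With six maternal assessments and two factors that is up to 2 × 6 = 12 parameters, which is more than the two for main effects but still small beside about 300 women.

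A reader might extend the fix to a stratified risk ratio for the IOM category. The documents do not support that here. D.16 gives no primary model for that outcome, its limits already depend on pre-pregnancy BMI, and no gain was computed for it.

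**Conclusion.** The gap is real and its effect is small. The stated primary model and the covariate list both omit the stratification factors, and the plan does not say whether they will be used. If they are prognostic beyond baseline, the test is slightly conservative and the interval wider than necessary: by 0.1% to 2.6%, or 0.1 to 1.6 power points, at assumed R-squared values of 1% to 5%. Gains of about 5 to 6 points for GWG and birthweight need the strata alone to account for the full 20%. The gain is smallest where a baseline value already carries the stratum information, as for glucose.

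These sizes rest on assumed R-squared, stratum shares and correlations; the documents supply none of them.

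A reader might infer that the omission biases the effect, inflates false positives or undercuts the stated power. It does none of these: blocking balances the strata, the error runs the other way, and the five detectable differences in the first table reproduce without covariates. Nor should a reader infer that every power figure is confirmed. Caloric intake, CRP and the IOM outcome do not reproduce, for reasons unrelated to the strata.

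**What to change.** In D.16, name age group and pre-pregnancy BMI class, coded as in the randomisation, as fixed effects in the primary models for Aims 1 to 4, with period interactions where the outcome is repeated. State that the 15% change-in-estimate criterion applies only to secondary or sensitivity models.

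The cost is two or three sentences and roughly 2 to 12 degrees of freedom. Both factors must already be recorded in order to randomise, so no new data or participants are needed.
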